Main Exclusion Criteria	
Subjects who meet any of the following criteria will be excluded from participation in this study:
 
 
1. Other than psoriasis, any clinically significant (as determined by the investigator) cardiac, endocrinologic, pulmonary, neurologic, psychiatric, hepatic, renal, hematologic, immunologic disease, or other major disease that is uncontrolled.
 
2. Forms of psoriasis other than chronic plaque-type (e.g., Pustular erythrodermic and/or guttate psoriasis) or drug induced psoriasis
 
3. Subjects who previously used any biologic agent for psoriasis.
 
4. Use of oral systemic medications for the treatment of psoriasis within 4 weeks (includes, but not limited to, oral corticosteroids, methotrexate, acitretin and cyclosporine).
 
5. Patient used topical therapies to treat psoriasis on the hands and/or feet within 2 weeks of the Baseline Visit (includes, but not limited to, topical corticosteroids, vitamin D analogs, or retinoids).
 
6. Patient received UVB phototherapy within 2 weeks of Baseline.
 

Study Drug Dosage and Administration	
All patients will receive OTEZLA® 30mg twice daily at week 0 (baseline) through week 8. At week 8, patients who achieved between PASI 25-74 response will receive 4 weeks of add-on Enstilar® (calcipotriene and betamethasone dipropionate) Foam, 0.005%/0.064% once daily in addition to continuing OTEZLA® 30mg twice daily.
 
At week 12 (after 4 consecutive weeks of Enstilar® add on therapy), Enstilar® will be discontinued and patients will continue OTEZLA® 30mg twice daily as monotherapy through week 16.

	Patients who achieve PASI 75 at week 8 will remain enrolled on OTEZLA® 30mg BID monotherapy through week 16.
Study Endpoints	
Primary Endpoints:
 
PASI 75 at week 12 for patients in the OTEZLA® + Enstilar® combination arm.
 
Secondary Endpoints:
 
PASI 25-74 at week 8.
 
PASI, PGA, BSA, PGAxBSA and DLQI improvement at week 8
 
PASI, PGA, BSA, PGAxBSA and DLQI improvement at week 12
 
PASI PGA, BSA, PGAxBSA and DLQI improvement at week 16
 
Serious Adverse Events (SAE's)

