## **5. INVESTIGATIONAL PLAN**

### **5.1 Overall Study Design and Plan**

50 subjects affected with plaque psoriasis with body surface area greater than or equal to 10%, and physician's global assessment greater than or equal to 3 and PASI greater than or equal to 12 will receive OTEZLA® 30 mg twice daily for 8 weeks.

Patients who do not achieve at least a PASI 25 at week 8 will be discontinued from treatment and study procedures.

At week 8, subjects who have achieved a PASI 25-74 will receive Enstilar® (calcipotriene and betamethasone dipropionate) Foam, 0.005%/0.064% once daily for 4 weeks in addition to continuing OTEZLA® BID. These patients will then discontinue Enstilar® at week 12 and remain on OTEZLA® monotherapy through week 16.

Patients who achieve PASI 75 at week 8 will remain enrolled in the study and continue OTEZLA® 30mg BID through week 16. These subjects will not receive Enstilar® add-on therapy.

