### **5.6.10 Early Discontinuation Procedures**

Subjects will be prematurely discontinued from the study under the following conditions:

1. Subject does not reach PASI 25 or greater at week 8
2. Subject requests to withdraw from the study.
3. Subject is noncompliant with protocol schedule, restrictions, and/or requirements as deemed per investigator.
4. Subject experiences an adverse event that makes it difficult or intolerable for the subject to continue treatment, or increases risk to the subject, or interferes with the investigator's ability to clinically evaluate the progress of the subject's treatment.
5. Subject begins an unapproved concomitant therapy for psoriasis or another medical condition that may increase risk to the subject if continuing study treatment.
6. Subject cannot be reached / lost to follow-up.
7. The study investigator suspends or terminates the study.
8. Other unanticipated reason.

Any subject who prematurely discontinues the study should complete the week 16 (End of Study) assessments. Any subject who withdraws consent to participate in the study will be removed from further treatment and/or study observation immediately upon the date of request.

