## 8.2 Statistics

It is desired to enroll 50 patients based on the data from the Esteem trial which showed 55% of subjects achieved between a PASI 25- PASI 74 response at week 8, hence it is expected that 30-40 patients will fit the continuation criteria at week 8 and be followed through week 16.

The study will analyze data based on the non-responder imputation (NRI) method. This will be performed for each arm of the study (PASI 75 responders at week 8 and PASI 25-74 responders at week 8. Subjects who do not complete week 16 assessments will be classified as non-responders.

Since this is a pilot study with no formal hypothesis testing, statistical power/sample size is not formally presented in this protocol.

Analysis will be performed by the Investigator on proportion of subjects achieving Psoriasis Area Severity Index (PASI) 75 response at week 12

The investigator will also analyze PASI 25-74 at week 8, PASI, PGA, BSA, PGAxBSA and DLQI improvement at week 8, BSA, PGA and BSA x PGA and DLQI improvement at week 12. PASI, BSA, PGA, BSA x PGA and DLQI at week 16. This analysis will be done separately for both cohorts (PASI 75 responders at week 8 and PASI 25-74 responders at week 8) using summary statistics. The Investigator will also analyze SAE's by cohort.

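### The one explicit non-responder rule is tied to week 16 and does not say which visit's outcome it governs, so a measured week-12 responder could be counted as a failure on the week-12 primary endpoint

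*Combined protocol and SAP*

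**What the plan says.** - **Endpoint.** The synopsis defines the primary endpoint as "PASI 75 at week 12 for patients in the OTEZLA® + Enstilar® combination arm". Section 8.2 sets the matching analysis as the "proportion of subjects achieving Psoriasis Area Severity Index (PASI) 75 response at week 12".
- **Missing data.** Section 8.2 states: "The study will analyze data based on the non-responder imputation (NRI) method". It applies this to both week-8 response cohorts and then adds the only explicit trigger in the documents: "Subjects who do not complete week 16 assessments will be classified as non-responders". No visit or outcome is attached to that classification.
- **After week 12.** Section 5.1 says of the add-on subjects: "These patients will then discontinue Enstilar® at week 12 and remain on OTEZLA® monotherapy through week 16". The schedule of events (section 8.3) lists PASI separately at weeks 8, 12 and 16.
- **Leaving early.** Section 5.6.10 lists among the reasons for discontinuation: "Subject cannot be reached / lost to follow-up". A subject who withdraws consent "will be removed from further treatment and/or study observation immediately upon the date of request". For early leavers in general: "Any subject who prematurely discontinues the study should complete the week 16 (End of Study) assessments".
- **Further plan.** Section 8.2.1 allows a separate statistical plan at the sponsor-investigator's discretion. The documents contain none.

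**The concern.** NRI is meant to fill in a value that is missing. Taken at its word, the week-16 sentence can instead overwrite a value that was measured, because of something that happened up to four weeks later. Those four weeks come after the foam has been stopped, so completing them says nothing about whether the add-on brought a partial responder to PASI 75 by week 12, which is the study's question.

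The study has no formal test, so the reported week-12 proportion is its main result. If the rule deciding who counts as a responder can be read in two ways, two analysts could report different primary results from the same data.

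**Working it through.** **1. The passages side by side.** The outcome is fixed at week 12 (synopsis; section 8.2). The trigger is fixed at week 16 (section 8.2). Because PASI is scheduled at both visits, a subject can have the first result without the second. Three routes lead there for a week-12 responder: withdrawal of consent, loss to follow-up and a missed week-16 visit. The exit that the synopsis (Study Duration) names for add-on subjects at week 12 is for those without PASI 75; they are failures already and do not matter here.

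**2. Cohort size.** Section 8.2 cites 55% with PASI 25-74 at week 8 and enrolment of 50: 0.55 × 50 = 27.5, taken as 28. The plan's own figure is 30-40 subjects meeting the continuation criteria. The 55% alone does not reproduce it, since 30/50 = 60% and 40/50 = 80%. If continuation also includes week-8 PASI 75 responders, as the design allows, a further 5% to 25% of subjects would be needed, a rate the documents do not give. The figure can be neither confirmed nor refuted, and the point does not depend on it. I use n = 28, 30 and 40, with 40 as an upper value for the add-on cohort.

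**3. Cost of one recoded responder (literal reading).** The shift is 1/n, whatever the true response rate:

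- n = 28: 1/28 = 3.6 points
- n = 30: 1/30 = 3.3 points
- n = 40: 1/40 = 2.5 points

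**4. General form.** Let p be the week-12 PASI 75 proportion and d the share of week-12 responders without week-16 assessments. The literal rule reports p(1 − d), a shift of −p·d, which is never upward. The documents give neither p nor d. With assumed p = 50% and d = 10%, the report is 0.50 × 0.90 = 45%. Over assumed ranges p = 30-70% and d = 5-20%, the fall runs from 0.30 × 0.05 = 1.5 points to 0.70 × 0.20 = 14 points. The upper end needs about four recoded responders at n = 28 (0.14 × 28 = 3.9).

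**5. Illustration.** Assume a 50% week-12 rate and 0, 1 or 2 recoded subjects (exact Clopper-Pearson 95% intervals):

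| n | 0 recoded | 1 recoded | 2 recoded |
|---|---|---|---|
| 28 | 50.0% (30.6-69.4) | 46.4% (27.5-66.1) | 42.9% (24.5-62.8) |
| 30 | 50.0% (31.3-68.7) | 46.7% (28.3-65.7) | 43.3% (25.5-62.6) |
| 40 | 50.0% (33.8-66.2) | 47.5% (31.5-63.9) | 45.0% (29.3-61.5) |

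The largest shift shown is 2/28 = 7.1 points. The interval half-width with none recoded is (69.4 − 30.6)/2 = 19.4 points at n = 28 and (66.2 − 33.8)/2 = 16.2 points at n = 40.

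**6. The narrower reading.** If the sentence governs week-16 outcomes only, the week-12 shift is zero for every n, p and d.

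**The case against.** The strongest reply is that imputation, by convention, fills missing values, so an observed week-12 PASI leaves nothing to impute. On that view the week-16 sentence merely describes subjects who miss the last visit. It does not mention week 12 or the primary endpoint, and it follows a statement about both cohorts, one of which is outside the primary endpoint. This reading is reasonable and cannot be excluded. Nor is it written down: the sentence sits in the general NRI paragraph with no limit on its scope, and an explicit rule would normally be followed as it stands. What remains is an ambiguity about the primary result.

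The second reply is that few subjects are exposed. Recoding needs an add-on subject who reaches PASI 75 at week 12, leaves in the next four weeks and has no End of Study assessment, and section 5.6.10 asks early leavers for that assessment. This stands as a limit on size. It cannot reach subjects who are lost or have withdrawn consent, and the documents do not say whether an early End of Study visit counts as completing week 16.

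Third, the study is a pilot without a formal test, and the error could only lower the reported rate. Both statements are correct, and both reduce the weight of the point.

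Two stronger readings should be resisted. A reader might infer that the plan redefines its primary endpoint as PASI 75 at week 12 plus completion of week 16. The documents do not support that: the synopsis and section 8.2 both state the endpoint as week 12, and the composite arises only if the trigger is applied literally. A reader might also infer that a missing week-12 PASI has no rule at all; the general NRI statement covers it by convention.

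**Conclusion.** The point holds as an ambiguity in how the primary outcome is classified, and it should be fixed. The one explicit non-responder rule does not name the outcome it governs, and on its literal reading it turns measured week-12 successes into failures. Section 8.2.1 does not cure this, because it only permits a further plan.

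On the literal reading, the loss per recoded responder is 3.6, 3.3 or 2.5 points at n = 28, 30 or 40; this rests only on the cohort size. Anything beyond that rests on assumptions: with 0 to 2 recoded, the shift is 0 to 7.1 points, well inside the sampling uncertainty of about 16 to 19 points either side at an assumed 50% rate. The number affected is not given, is probably small and may be zero. No success decision turns on it; the effect is on the reported proportion.

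**What to change.** Replace the week-16 sentence in section 8.2 with:

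> Non-response is imputed visit by visit: for each responder outcome, a subject with no PASI assessment at the visit being analysed is a non-responder at that visit. For the primary endpoint this visit is week 12, and an observed week-12 result is kept whether or not week 16 is completed.

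The cost is one sentence replaced by two. No data or visits are added, since PASI is already scheduled at weeks 12 and 16. Subjects without a week-12 PASI still count as non-responders, so missing cases are not dropped in the treatment's favour. The text covers responder outcomes only and leaves the summaries of the continuous measures as they are.

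A rule on End of Study assessments made before week 12 should be added only together with a stated week-12 visit window. The schedule of events gives no windows, and without one such a rule could discard a PASI measured a day or two early.

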Study Duration	
16 weeks
 
The subject may continue to participate in this study until one of the following occurs:
 
 
• Subject has not achieved PASI 25 at week 8
 
• The subject experiences a significant or serious adverse event related to study drug;
 
• Subjects who initially achieved PASI 75 at week 8 and lose response by week 12 may withdraw at their own request.
 
• Subjects who received Enstilar® add-on therapy for 4 weeks and have not achieved PASI 75 at week 12 may withdraw at their own request.
 
• The subject is not willing to continue participation in the study;
 
• Subject completes 16 weeks of study drug and evaluations
 
• The Sponsor decides to terminate the study for any reason.
 

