### **5.5.1.5 OTEZLA® Dosage Adjustments**

If an SAE or an adverse event that is thought to be related to OTEZLA® and is not alleviated by symptomatic intervention, OTEZLA® will be discontinued.

Subjects who permanently discontinue OTEZLA® therapy under this protocol should receive standard care of psoriasis treatment as prescribed by their physician.

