### 8.2.1 Additional Statistical Considerations

Additional statistical procedures may be detailed in and performed according to a separate statistical plan at the discretion of sponsor-investigator.

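### Section 8.2 plans no SAE summary for treated subjects below PASI 25 or without a week-8 PASI, and names no all-treated denominator for the week-8 results

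*Combined protocol and SAP*

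**What the plan says.** All 50 subjects are to take OTEZLA from baseline to week 8 (Synopsis, Study Drug Dosage and Administration; section 5.1). At week 8 they divide three ways: PASI 75 responders stay on OTEZLA alone, subjects at PASI 25-74 add Enstilar for four weeks, and subjects below PASI 25 leave the study.

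The Synopsis lists as secondary endpoints the PASI 25-74 proportion at week 8, "PASI, PGA, BSA, PGAxBSA and DLQI improvement at week 8", and SAEs. None of these is restricted to a cohort.

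Section 8.2 lists the outcomes by visit and continues: "This analysis will be done separately for both cohorts (PASI 75 responders at week 8 and PASI 25-74 responders at week 8"). These summaries are descriptive. For safety, the section adds: "The Investigator will also analyze SAE's by cohort". The non-responder rule is set out for the same two groups: "Subjects who do not complete week 16 assessments will be classified as non-responders". On numbers, the section cites 55% at PASI 25-74 at week 8 in an earlier trial, "hence it is expected that 30-40 patients will fit the continuation criteria at week 8 and be followed through week 16".

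No all-treated, safety or full analysis set is defined. Section 8.2.1 allows further statistical procedures in a separate plan, but only "at the discretion of sponsor-investigator".

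**The concern.** Every treated subject contributes eight weeks of OTEZLA exposure, or less if he or she withdraws, before any cohort exists. The only groups named for analysis are then formed from the week-8 result. Two consequences follow.

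- **SAEs.** A subject below PASI 25, or with no week-8 PASI, belongs to neither cohort, so an SAE in that subject falls in no planned table. The omission need not be random. The Synopsis (Study Duration) gives as a reason to leave: "The subject experiences a significant or serious adverse event related to study drug". Section 5.5.1.5 adds that after a related event that "is not alleviated by symptomatic intervention, OTEZLA® will be discontinued". A subject whose related SAE ended participation before week 8 is therefore among those with no planned summary.
- **Week-8 outcomes.** If the cohort split governs the week-8 list, improvement on OTEZLA is shown only in subjects selected for having improved. PASI improvement is at least 25% in one cohort and at least 75% in the other by definition, and the PASI 25-74 endpoint is 100% in one and 0% in the other. Neither describes what eight weeks of OTEZLA did in the subjects who took it.

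The trial has no hypothesis test, so descriptive summaries are its whole output and their denominators carry the interpretation.

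**Working it through.** **Who is in which group**

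| Treated subject | PASI 25-74 cohort | PASI 75 cohort | Planned SAE summary |
|---|---|---|---|
| PASI 25-74 at week 8 | yes | no | yes |
| PASI 75 or more at week 8 | no | yes | yes |
| Below PASI 25 at week 8 | no | no | none |
| No week-8 PASI | no | no | none |

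The non-responder rule does not fill the last two rows. It assigns a response status, within the two cohorts, and it cannot place an SAE or supply a change score.

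**Inputs for the size of the gap**

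- Enrolment 50, PASI 25-74 rate 55%, and forecast of 30-40 continuing: section 8.2.
- Week-8 PASI 75 rate, p: not given in the documents. I use 5% to 33.1% as an assumed range. The top value is the week-16 rate cited in section 3.2, used only as a high case.
- Both rates are taken as shares of all 50.

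**The plan's own figure.** 50 × 0.55 = 27.5. The 30-40 forecast does not follow from the 55% alone. If it means both cohorts together, it needs a further 30 − 27.5 = 2.5 to 40 − 27.5 = 12.5 PASI 75 responders, so p = 2.5/50 = 5% to 12.5/50 = 25%. If it means the PASI 25-74 group alone, it implies 30/50 = 60% to 40/50 = 80%, not 55%. The text does not settle which is meant.

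**Number in neither cohort, from the 55%:** 50 × (1 − 0.55 − p) = 50 × (0.45 − p).

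| Assumed p | In neither cohort | Share of 50 |
|---|---|---|
| 5% | 20.0 | 40% |
| 10% | 17.5 | 35% |
| 20% | 12.5 | 25% |
| 25% | 10.0 | 20% |
| 33.1% | 5.95 | 11.9% |

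**From the forecast instead**

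- Both cohorts together: 50 − 40 = 10 to 50 − 30 = 20.
- PASI 25-74 group alone: 10 to 20, less 50p. With 30 in that group and p = 33.1%, 20 − 16.55 = 3.45. With 40 in that group the remainder reaches zero at p = 10/50 = 20%.

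**The case against.** **The word 'only' is not in the plan.** Section 8.2 says by cohort and expressly excludes no one. The cohort sentence follows the week-16 list and might refer to that list alone. The PASI 25-74 endpoint makes sense only over all enrolled subjects, which suggests that the author did not mean the split to govern every item. This stands for week 8: on that reading the defect is an unstated denominator, not a planned exclusion. It does not help with SAEs, because that sentence stands alone and says by cohort on either reading.

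**The stakes are limited.** The objectives centre on the combination, subjects below PASI 25 never receive Enstilar, and this is a pilot. That stands too, and it limits the weight of the point. But week-8 improvement and SAEs are listed endpoints with no cohort restriction.

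**SAEs are still captured.** Section 6 records adverse events from consent and requires SAE reports within 24 hours. True; what is missing is a planned summary, not the data.

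**Three stronger readings that the documents do not support**

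- *That the plan inflates week-8 improvement by a known number of points.* No pooled two-cohort mean is planned, and each cohort is labelled by its response. Nor is the direction uniform. As an illustration, take percent PASI improvement as normal, with 55% at PASI 25-74 and rate p at PASI 75 or more. The PASI 25-74 cohort mean is then 45.2% against 31.7% in all treated at p = 5%, but 50.5% against 52.8% at p = 25%, and 52.3% against 61.5% at p = 33.1%. At those last two rates the model also puts 7.6% and 10.6% of subjects above 100% improvement, which is impossible. It is no basis for a figure.
- *That every early SAE is lost.* An early SAE in a subject who reaches week 8 with PASI 25 or better is counted in that subject's cohort.
- *That the gastrointestinal warning in section 5.5.1.2 shows SAEs will cluster in the gap.* It describes severe events in postmarketing reports. Section 6 separates severity from seriousness, and only SAEs are planned for analysis.

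**Conclusion.** The point holds and should be fixed.

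- **SAE part: firm.** Followed as written, the plan has no summary for SAEs in treated subjects below PASI 25 or without a week-8 PASI, including a related SAE that caused early withdrawal.
- **Week-8 part: depends on the reading.** Either the improvement endpoints are shown only in subjects selected on week-8 response, or their denominator is not stated. Both call for the same change.
- **Size: not fixed by the documents.** At assumed week-8 PASI 75 rates of 5%, 25% and 33.1%, about 20, 10 and 6 of 50 subjects are in neither cohort. The number is 10-20 if the 30-40 forecast covers both cohorts, and possibly near zero if it covers the PASI 25-74 group alone. The gap in the plan does not depend on which applies.

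A reader might infer that the main result is compromised. It is not: the primary endpoint is defined in the PASI 25-74 cohort, and everyone who receives Enstilar under the protocol is in that cohort, so the safety summary of the combination is complete.

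**What to change.** In section 8.2:

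1. Report four week-8 categories (below PASI 25, PASI 25-74, PASI 75 or more, and missing) as proportions of all subjects who received at least one OTEZLA dose. Count missing in the denominator and not as a response.
2. Summarise week-8 PASI, PGA, BSA, PGAxBSA and DLQI improvement in all treated subjects with a week-8 assessment, stating the number missing, beside the cohort summaries.
3. Report SAEs for all treated subjects, with a third group (below PASI 25 or no week-8 PASI) beside the two cohorts.
4. Keep the cohort-specific summaries at weeks 12 and 16.

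The cost is wording and one extra column or group per table. The schedule of events already includes the week-8 assessments and adverse event collection, so no new data are needed. The downside is that the week-8 result may look less favourable.

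A separate matter to reconcile: section 5.1 takes subjects below PASI 25 out of study procedures at week 8, while section 5.6.10 asks anyone who discontinues early to complete the End of Study assessments. The four changes above do not depend on how that is settled.
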